12.0 CRITERIA FOR THERAPEUTIC RESPONSE/OUTCOME ASSESSMENT

Positive lesions on ⁸⁹Zr-DFO-MSTP2109A will be defined visually as a focus of accumulation of radioactivity that is deemed to not be physiologic and is higher than adjacent or contralateral background. Antibody scan will be read blinded from clinical history and conventional imaging modalities. Two different experienced, blinded readers will visually analyze the ⁸⁹Zr-DFO-MSTP2109A scans, and SUVmax/mean will be determined in lesions identified and in normal organs and blood pool. To study the accumulation and biodistribution of ⁸⁹Zr-DFO-MSTP2109A in patients with progressive prostate cancer, the accumulation of ⁸⁹Zr-DFO-MSTP2109A will be assessed for each site and compared with the baseline radionuclide bone scan, FDG PET/CT, CT, and/or MRI imaging. The definition of a positive lesion will be a lesion identified by an experienced reader on conventional imaging CT/MRI, bone scan, and/or FDG scan consistent with metastatic disease, as is currently done clinically. Lesions on ⁸⁹Zr-DFO-MSTP2109A or conventional imaging will be read in a scale of 1 to 5, 1= negative, 2 = probably negative, 3= not sure, 4= probably positive and 5= definitively positive. Once this is done, a consensus master list of lesions will be created that compares all imaging conventional imaging modalities(CT/MRI, FDG PET, bone scan), only those lesions that are conspicuously positive (i.e., "4 or 5") by imaging will be considered as a positive site of disease. Discrepant findings between findings on conventional imaging and ⁸⁹Zr-DFO-MSTP2109A modalities will be considered false positive or false negative. Although it would be ideal to biopsy any site that is considered abnormal this is not logistically feasible or ethically acceptable. Successful imaging will be considered a sensitivity of detection of $\geq 75\%$ of patients that are STEAP1 positive. One or 2 non-blinded readers (access to clinical, laboratory and imaging data) will identify "positive lesions".

As a first level, we will compare site by site. Since the individual modalities are based on different mechanisms of uptake, they may not have exact correspondence in space, since bone scan is a 2D modality and looks at bone reaction and ⁸⁹Zr looks at tumor antigen expression and is a 3D modality.

For this purpose, we have made a list of standardized anatomic sites, to make sure that a positive

MEMORIAL SLOAN-KETTERING CANCER CENTER IRB PROTOCOL

IRB#:12-178 A(3)

lesion would have a positive ^{89}Zr -DFO-MSTP2109A uptake. As a second level, we will compare lesion by lesion. Sensitivity and specificity of the imaging modalities will be compared in those patients receiving the better/"adequate" antibody mass. The "better/adequate" dose is defined as that which will allow us to visualize the targeted number of lesions defined and will consist of either 10 or 20 mg of DFO-MSTP2109A antibody.

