2.2 Secondary Objectives

- To determine the better/"adequate" ⁸⁹Zr-DFO-MSTP2109A mass amount for tumor imaging (10 or 20 mg) .
- To determine optimal time relative to ⁸⁹Zr-DFO-MSTP2109A administration for tumor imaging.
- To use quantitative biodistribution data of ⁸⁹Zr-DFO-MSTP2109A uptake to perform dosimetry estimates.
- To correlate ⁸⁹Zr-DFO-MSTP2109A uptake in tumors with STEAP1 antigen expression by IHC
- To explore whether ⁸⁹Zr-DFO-MSTP2109A PET imaging results are related to patient outcome in patients being treated with DSTP3086S.

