Images will be analyzed with ROI and SUVmean and max measurements will be obtained. The serial quantitative data obtained over the various organs of interest (heart, liver, spleen, kidney, lung and any other organ that exhibits uptake will be collected. These data can then be utilized to determine organ time activity curves and the dosimetry can be calculated. Uptake and clearance values will be summarized using descriptive statistics (mean, median standard deviation. Once the biodistribution and pharmacokinetics have been characterized, subsequent patients will not require serial imaging and pharmacokinetics, but rather will have a single scan at an optimal time point determined based on the patients in cohort 1A and or cohort 1B. We will determine the time at which the greatest number of lesions are seen. This is likely to be between 3-8 days, but choice will be based on the first Cohort 1 patients' data, using the most frequent day at which the most lesions are seen and/or at times at which best contrast is observed determined visually. Thus, for the remainder of the patients in Cohort 2, PET scan will be performed once. The timing of this scan will be determined based on findings from Cohort 1A and/or 1B, as described above.

Infusion reactions with MSTP2109A intact IgG have not been evaluated. Infusion reaction to the ADC DSTP3086S antibody drug conjugate in 18 patient treated thus far have been minor and not clinically significant (i.e. none or Gr1). In the event of fever, rigors, shortness of breath, or other evidence of infusion reaction, patients may receive diphenhydramine 25-50 mg IV and Tylenol 650 mg PO as felt to be clinically appropriate by the treating physician. The emission data are typically acquired for 3–10 minutes per bed position depending upon the time post-injection and visual quality of the images. Index lesions will be identified based on the patient's conventional diagnostic imaging.

Images will be stored as Digital Imaging and Communications in Medicine (DICOM) on the PACS and HERMES. Images to be sent out to Genentech will be burned on a CD or equivalent by patient. All images will be anonymized according to institutional policy with the patients code used as identifiers.

No decision on the patients' health care management will be made on the basis of Imaging with ⁸⁹Zr-DFO-MSTP2109A.

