14.3 Secondary objectives

One of our secondary exploratory objectives is to estimate the uptake in tumors. We will present lesion-based summary statistics for the uptake adjusted for clustering. Another secondary objective is to correlate ⁸⁹Zr-DFO-MSTP2109A imaging to response to treatment in those patients recruited to protocol 11-016 DSTP3086S ADC. Outcome measures to be correlated include those that are outlined in the parent protocol 11-016 and include PSA response, RECIST response, presence or absence of new bone scan lesion and progression free survival. We will use Kaplan-Meier estimates and 95% confidence intervals to correlate these outcomes with imaging response.

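### The only rule for lesion SUV, read directly, measures it in lesions found on the tracer scan, so tumor uptake may be summarised over lesions selected for high uptake

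*Combined protocol and SAP*

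**What the plan says.** Section 12.0 defines a positive tracer lesion visually, as a non-physiologic focus that "is higher than adjacent or contralateral background". It also states: "Antibody scan will be read blinded from clinical history and conventional imaging modalities". Two such blinded readers analyse the tracer scans and, in the same sentence, "SUVmax/mean will be determined in lesions identified and in normal organs and blood pool". This is the only instruction that says in which lesions SUV is measured.

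Other text bears on the lesion set without settling it:

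- Section 12.0 continues that tracer accumulation "will be assessed for each site and compared with the baseline radionuclide bone scan, FDG PET/CT, CT, and/or MRI imaging". It does not name SUV there.
- Section 12.0 also plans a consensus master list of conventional-imaging lesions (only scores 4 or 5 count as disease) and one or two non-blinded readers.
- Section 9.3 says: "Index lesions will be identified based on the patient's conventional diagnostic imaging". It does not say what is measured in them. Its general sentence on ROI-based SUVs is followed by a list of organs.
- Section 14.3 says: "We will present lesion-based summary statistics for the uptake adjusted for clustering". It does not say which lesions.
- Section 2.2 aims to correlate "uptake in tumors with STEAP1 antigen expression by IHC".

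**The concern.** A reader blinded to CT, MRI and bone scan cannot draw a region on a lesion known only from those scans. On the direct reading of section 12.0, a known lesion that the tracer misses has no SUV, and a patient with no visible lesion contributes no lesion uptake at all. A focus seen only on the tracer, which section 12.0 would class as a false positive, does get one.

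Lesions would then enter the uptake data because their uptake was high enough to be seen. That is selection on the variable being summarised. It pushes the mean up and narrows the range of uptake, which lowers its correlation with STEAP1 expression or response. The bias grows as the tracer performs worse. The clustering adjustment in section 14.3 deals with several lesions per patient, not with this selection.

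At stake are the descriptive uptake summary and any SUV-based correlation. Section 14.2 gives the link between tracer imaging and response to the antibody drug conjugate as the main emphasis, so these secondary results matter to the study's purpose.

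**Working it through.** **The plan's own figures.** The plan states none for lesion SUV or the STEAP1 correlation. Its only operating figures, in section 14.2, reproduce:

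- Probability of opening cohort 1B, i.e. 3 or fewer of 6 patients positive: 0.8208 at a true rate of 40% (plan: more than 82%) and 0.1694 at 75% (plan: less than 17%).
- Cohort 2 half-width: 1.96 × √(0.75 × 0.25 / 15) = 0.219 (plan: 22%).

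None of these depends on SUV.

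**Inputs for the selection effect, all assumed because the documents give none.**

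- Lesion SUV is log-normal, with SD of log SUV (σ) from 0.4 to 0.8.
- Share of lesions detected (d): 90%, 75%, 50% or 20%. Section 14.2 uses 20% as the minimum for a patient to count as positive; it is not an expected lesion detection rate.
- True correlation (ρ) between log SUV and STEAP1 expression: 0.5 as the central case.
- Detection is a sharp cut: the share d with the highest SUV is seen.

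**Formulas.** Let c = Φ⁻¹(1 − d) and λ = φ(c)/d.

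- Shift in mean log SUV, in SDs: λ
- Ratio of observed to true arithmetic mean SUV: Φ(σ − c)/d
- Ratio of observed to true SD of log SUV: u = √(1 − λ(λ − c))
- Observed correlation: ρu / √(1 − ρ² + ρ²u²)

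**Worked case, d = 0.75.** c = −0.6745 and λ = 0.424. The mean ratio is Φ(1.0745)/0.75 = 0.8587/0.75 = 1.14 at σ = 0.4, and Φ(1.4745)/0.75 = 0.9298/0.75 = 1.24 at σ = 0.8. u = 0.731. With ρ = 0.5, the observed correlation is 0.5 × 0.731 / √(0.75 + 0.25 × 0.534) = 0.366/0.940 = 0.39.

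| Lesions detected | Shift in mean log SUV (SD) | Mean SUV ratio, σ 0.4 to 0.8 | Observed correlation if true 0.3 / 0.5 / 0.7 |
|---|---|---|---|
| 90% | 0.20 | 1.06 to 1.09 | 0.26 / 0.44 / 0.64 |
| 75% | 0.42 | 1.14 to 1.24 | 0.22 / 0.39 / 0.58 |
| 50% | 0.80 | 1.31 to 1.58 | 0.19 / 0.33 / 0.51 |
| 20% | 1.40 | 1.65 to 2.42 | 0.15 / 0.26 / 0.42 |

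A simulation with 10 lesions per patient and an intraclass correlation of 0.4 agreed to within about 0.01 on the shift and the correlations.

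**Relaxing the sharp cut.** Suppose detection follows a score that correlates 0.7 with log SUV (an assumption), with noise unrelated to expression. The mean ratio becomes Φ(0.7σ − c)/d, and u² becomes 1 − 0.49 λ(λ − c). A true 0.5 is then observed as 0.45, 0.43 and 0.41 at 75%, 50% and 20% detection, and a true 0.7 as 0.65, 0.63 and 0.61. At 20% detection the mean ratio is 1.44 to 1.95.

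**With SUV in every known lesion.** The selection is gone: the shift is 0, the mean ratio is 1, and the correlation keeps its true value.

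**The case against.** The strongest reply is that the plan never says only. The word identified is also used for conventional imaging in sections 9.3 and 12.0, accumulation is to be assessed at each site, index lesions come from conventional imaging, and non-blinded readers are available. This stands in part: a reader might infer that SUV is expressly confined to tracer-positive foci, and the documents do not go that far. But none of this text orders an SUV in a tracer-negative lesion, and section 14.3 leaves its set open. Two different lesion sets therefore comply with the plan and would give different answers.

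Three further inferences are tempting and not supported:

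- *That the whole STEAP1 analysis is truncated.* Section 9.3 relates presence of STEAP1 in a lesion to its imaging result, and a tracer-negative lesion has a result. Only an SUV-based correlation is exposed. Section 6.2 also requires STEAP1-positive tissue, which narrows the expression range under any SUV rule.
- *That low-uptake lesions are dropped from the response analysis.* Section 14.2 intends to evaluate response in all available lesions, and section 14.3 relates outcome to imaging response without specifying an SUV model. The exposure exists only where SUV is the uptake measure.
- *That the choice between 10 and 20 mg is biased.* Sections 4.2, 12.0 and 14.2 base it on lesion detection, with pharmacokinetics and normal-organ uptake as supporting evidence. No SUV comparison between masses is planned.

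The objection to the size also stands. Visual detection against local background is not a sharp SUV cut, so the table's figures are upper bounds in that respect.

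**Conclusion.** The point holds as a cheap improvement to secondary, exploratory analyses. Read directly, the one lesion-SUV instruction selects lesions on uptake, and no other section corrects it. Under that reading, mean tumor SUV would tend to be overstated and SUV-based correlations weakened.

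The size cannot be fixed from the documents. For a log-SD within 0.4 to 0.8, the sharp-cut table is the upper bound. The effect is small if about 90% of lesions are seen and considerable at 50% or below. It shrinks further if detection follows SUV only loosely. Entry of tracer-only foci was not modelled. The primary endpoint, the antibody-mass decision and the positive/negative STEAP1 comparison do not depend on it.

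**What to change.** In section 12.0, state that once the blinded tracer read is locked, the non-blinded readers already planned measure SUVmax and SUVmean in every lesion on the conventional-imaging master list (score 4 or 5), whether or not the tracer read is positive, placing the region from the co-registered CT.

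In section 14.3, name this set as the basis for the uptake summary and for any SUV-based correlation with STEAP1 expression or outcome. List tracer-only foci separately. Flag lesions seen only on bone scan, and add a sensitivity summary that excludes them.

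The cost is some extra region drawing on scans already acquired, with no added patient procedure or radiation. SUVs will be less exact for bone-scan-only lesions, because section 12.0 notes that the 2D bone scan may not match the tracer scan in space, and for small lesions, because of the partial-volume effect noted in section 12.2. The reported mean uptake is likely to be lower.

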8.1 PRETREATMENT EVALUATION

- History and physical examination
- Laboratory studies (within 2 weeks before study entry):
 - Complete blood count
 - PSA

MEMORIAL SLOAN-KETTERING CANCER CENTER IRB PROTOCOL

IRB#:12-178 A(3)

- Serum BUN, creatinine, AST, ALT, total bilirubin, alkaline phosphatase, and albumin
- eGFR assessment
- Standard clinically indicated imaging studies (within 4 weeks before study entry or up to 2 weeks after entry, provided the patient has not received treatment). No intervening new therapy is allowed between conventional imaging studies and the ⁸⁹Zr-DFO-MSTP2109A
 - Bone scintigraphy
 - CT of chest, abdomen, and pelvis with contrast, unless contraindicated on clinical grounds (allergy or renal insufficiency). MRI is acceptable if CT is clinically contraindicated
 - Modified MRI of the pelvis, if clinically indicated
- If STEAP1 status is not known from prior testing patient archival tissue will be sent to Genentech to determine presence of STEAP1 antigen..

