Active lesions will be identified (Nuclear Medicine investigator and MM) based on conventional images and those thought to represent active disease based on review of the patients conventional images and treatment history (ie external radiation) will be considered as lesions for determination of antibody localization. A lesion will be considered present if there is greater localization than that expected based on blood pool distribution of the tracer. Given that at present we do not know the heterogeneity of the antigen between lesions or between primary and metastatic disease a patient will be considered positive if any of the active lesions are identified with the ^{89}Zr -DFO-MSTP2109A. We will, nonetheless tabulate the number of lesions and their status based on ^{89}Zr -DFO-MSTP2109A. When pathologic material that has been evaluated for the presence of STEAP1 is available for any specific lesion, we will correlate the presence of STEAP1 with imaging results.

Patients in Cohort 1A (and if performed Cohort 1B) will also have imaging at 4 time points post-injection to allow for selection of optimal imaging time and dosimetry determination. For these patients, top of skull to mid thigh scans will be acquired:

- Within one to four hours following injection of tracer on Day 1
- \sim 24 \pm 8 hours post-injection (Day 2)
- \sim 48–96 hours post-injection (once during Days 3–5)
- \sim 120–168 hours post injection (once during Days 6–8)

MEMORIAL SLOAN-KETTERING CANCER CENTER IRB PROTOCOL

IRB#:12-178 A(3)

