^a Screening evaluation should be performed following informed consent and within 4 weeks before study entry, except when noted otherwise. Evaluations performed as standard of care before informed consent but within the 4-week window need not be repeated.

^b Vital signs will be monitored prior to infusion and every 30 minutes for at least 2 h or later if the patient is still in the department for imaging.

^c Within 14 days laboratory studies include CBC, PSA, serum BUN, creatinine, AST, ALT, total bilirubin, alkaline phosphatase, albumin, blood glucose levels, and serum testosterone level. All laboratory studies are to be performed up to 2 weeks before study entry (serum testosterone level may be up to 4 weeks before study entry). At Days 6 to 8 CBC and comprehensive labs will be obtained.

^d Radiographic evaluations include bone scintigraphy, CT of chest, abdomen and pelvis (MRI is acceptable if CT is clinically contraindicated), and modified MRI of the pelvis, if clinically indicated. All radiographic studies are to be performed within 4 weeks before, or up to 2 weeks after study entry, provided the patient has not received treatment.

^e sample sent out to Genentech

^f Following injection with the ⁸⁹Zr-DFO-MSTP2109A tracer, the patients enrolled in the study (Patients Cohort 1 A and or 1B) will have serial whole-body PET-CT scans (WBS) performed to determine the biodistribution of the tracer. PET scans will be acquired: 1–4 hours following injection of the tracer, ~24 h \pm 8 h post-injection, ~48–96 hours post injection, and ~120–168 hours post injection. Slight variations in times due to scheduling or technical difficulties will not be considered violations

^g Whole body counts (WBC) using a probe will be performed during the imaging in the first 12 patients and the exact time recorded:

- Within 0.1 to four hours following injection of tracer on Day 1 (prior to voiding) and post voiding
- 24 \pm 8 hours post-injection (Day 2)
- ~48–96 hours post-injection (once during Days 3–5)
- ~120–168 hours post injection (once during Days 6–8)

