12.1 Bone Scan

Each lesion will be evaluated using the same 5-point scale. These findings will be compared with that of ^{89}Zr -DFO-MSTP2109A PET scanning.

Any discrepant reading of the antibody images or conventional images will require review of the images by both readers who will discuss and reach a consensus, if a consensus cannot be reached the finding shall be considered "not sure" and categorized as negative.

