14.1 BIOSTATISTICS

14.2 Primary Objective

The primary objective of this protocol is to determine the feasibility, safety and tolerability of single dose administration of ^{89}Zr -DFO-MSTP2109A antibody.

A patient with STEAP1 positive tumor will be considered antibody-imaging-positive if 20% or more of the active lesions are detectable (STEAP1 positivity is an eligibility criterion for protocol 11-016 which forms the basis of eligibility for this protocol; see section 6 for details). Active lesion means any lesion that was identified by conventional imaging methods and clinical data at baseline. We have selected a low threshold of 20% for this first imaging study for 3 reasons: 1) we do not know what the heterogeneity of antigen expression is within a number of lesions in the same patient; 2) we will consider positive any lesion based on conventional clinical imaging criteria, in which case some lesions considered positive may be false positive and more importantly 3) our main emphasis is to evaluate whether patients whose tumor images are positive with ^{89}Zr -DFO-MSTP2109A are more likely to have a response to the antibody based drug conjugate used under

MEMORIAL SLOAN-KETTERING CANCER CENTER IRB PROTOCOL

IRB#:12-178 A(3)

protocol 11-016. Thus, we do not want to discard this agent if we can use it as a **theranostic** (defined as an agent that is integrated into the drug development process so as to guide patient selection and drug development) for the development of the antibody base drug conjugate being used under protocol 11-016. Nonethe less, we intend to evaluate treatment response of all available lesions in this way we will maximize our ability to determine the relationship between uptake of antibody and response.

If, for any patient, there is evidence of an “antigen sink” based on rapid clearance < 50 h or $Vd > 3$ times plasma volume, we will consider a patient antibody-imaging-positive if 20% or more of the active lesions are visualized. The presence of an “antigen sink” may bind a significant amount of antibody and make less available for binding to tumor.

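### The readers who set the active-lesion list are not masked to the tracer scan, and the list need not be fixed before they see it

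*Combined protocol and SAP*

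**What the plan says.** **Blinding.** Section 12.0 states it in one direction: "Antibody scan will be read blinded from clinical history and conventional imaging modalities". Two such readers score the tracer scans. The same section defines a positive lesion by conventional imaging and says that "One or 2 non-blinded readers (access to clinical, laboratory and imaging data) will identify" these lesions. It does not say whether these readers may see the tracer scan.

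**Order.** Section 12.0 has lesions on the tracer scan or on conventional imaging scored from 1 to 5. It then says: "Once this is done, a consensus master list of lesions will be created". That list compares the conventional modalities, and only scores of 4 or 5 count.

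**Choice of lesions.** Section 9.3 takes as lesions "those thought to represent active disease based on review of the patients conventional images and treatment history". Section 14.2 says: "Active lesion means any lesion that was identified by conventional imaging methods and clinical data at baseline".

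**Timing.** Section 8.1 allows conventional imaging "within 4 weeks before study entry or up to 2 weeks after entry", provided that no treatment has been given. The footnotes to Table 2 in Section 10.0 repeat this: "All radiographic studies are to be performed within 4 weeks before, or up to 2 weeks after study entry".

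**Use.** Under Section 14.2 a patient is positive if at least 20% of his active lesions are detected. Four or more positives among the 6 patients of Cohort 1A make imaging feasible; otherwise Cohort 1B opens. The Cohort 2 detection estimate is the proportion of positive patients among up to 15.

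**The concern.** The patient-level result is a ratio. The numerator comes from blinded tracer readers. The denominator comes from readers whose knowledge of the tracer result is not controlled. Section 12.0 rules out biopsy of every abnormal site, so in practice the list is the reference standard, and it also serves the sensitivity and specificity comparisons.

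Whether a conventional finding scores 3 or 4, or whether a treated lesion is still active, is a matter of judgement. A reader who knows which lesions took up the tracer may judge equivocal ones differently without intending to. The resulting bias would enter the Cohort 1A decision and the Cohort 2 estimate, and a confidence interval for a proportion does not cover it.

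**Working it through.** **1. The plan's own figures.** With X positives in 6 patients, P(X ≥ 4) = 15p⁴(1−p)² + 6p⁵(1−p) + p⁶.

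- p = 0.40: 0.1382 + 0.0369 + 0.0041 = 0.1792, so Cohort 1B opens with probability 0.8208. Section 14.2 states above 82%.
- p = 0.75: 0.2966 + 0.3560 + 0.1780 = 0.8306, so Cohort 1B opens with probability 0.1694. Section 14.2 states below 17%.
- Cohort 2 half-width at p = 0.75, n = 15: 1.96 × √(0.75 × 0.25 / 15) = 0.219. Section 14.2 states 22%.

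All three are reproduced. The plan's arithmetic is sound, but it takes the patient-level call as free of bias.

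**2. Can list choices change a call under the 20% rule?**

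| Detected / listed | Call | Change to the list | Result | Call |
|---|---|---|---|---|
| 1/6 = 16.7% | negative | one tracer-negative lesion left off | 1/5 = 20% | positive |
| 2/11 = 18.2% | negative | one tracer-negative lesion left off | 2/10 = 20% | positive |
| 1/6 = 16.7% | negative | one equivocal tracer-positive lesion admitted | 2/7 = 28.6% | positive |

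A single decision suffices for a patient just below the cut-off.

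**3. What could this do to the Cohort 1A gate?** The documents give no reclassification rate. Assume that a share f of truly negative patients is turned positive, so the apparent rate is p + (1 − p)f. From the plan's low rate, p = 0.40:

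| f (assumed) | Apparent rate | P(at least 4 of 6) | P(Cohort 1B opens) |
|---|---|---|---|
| 0 | 0.40 | 17.9% | 82.1% |
| 0.05 | 0.43 | 22.3% | 77.7% |
| 0.10 | 0.46 | 27.2% | 72.8% |
| 0.20 | 0.52 | 38.2% | 61.8% |

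**4. Cohort 2.** The same f shifts the expected proportion by (1 − p)f. At p = 0.40 and f = 0.05 to 0.20 this is 3 to 12 percentage points. At p = 0.75 and f = 0.20 it is 0.25 × 0.20 = 5 points.

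**5. Dependence on the definition.** Section 9.3 counts a patient as positive if any active lesion is seen. Under that rule, leaving off tracer-negative lesions changes nothing; only admitting an equivocal tracer-positive lesion to a list with no detected lesion could matter. The two definitions conflict and need reconciling.

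**The case against.** The strongest reply is that the plan already restricts the list. Sections 9.3, 12.0 and 14.2 draw it from conventional imaging, and Section 14.2 adds that it is a baseline list. Section 14.2 also accepts that some listed lesions may be false positives, which works against pruning. Section 12.0 classes disagreement between tracer and conventional imaging as false positive or false negative, and does not send it back to change the list. These points stand. They mean that a lesion seen only on the tracer scan should not enter. They restrict the source of the list, not what its authors know when they judge a doubtful lesion.

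Three stronger readings are tempting, and the documents do not support them.

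- *The list-setters are given the tracer scan.* The imaging data in Section 12.0 are not said to include it. Non-blinded most naturally means having what the tracer readers are denied. The gap is that tracer access is not excluded.
- *The consensus step mixes the two image sets.* Section 12.1 says "Any discrepant reading of the antibody images or conventional images will require review of the images by both readers". This most naturally covers two readers disagreeing within one image set.
- *The imaging window shows that baseline images follow the tracer scan.* The window runs from study entry, which is not equated with injection. Later acquisition is possible, but it would not show that the reader had seen the tracer result.

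Context also counts. This is a small single-arm feasibility study, tracer results guide no patient's care, and failing the first gate opens a second cohort.

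**Conclusion.** The concern holds in a limited form. The plan does not mask the list-setters to the tracer scan and does not require the list to be complete before they see it. The exposure is confined to equivocal conventional lesions (score 3 versus 4, active versus treated) in patients near the 20% cut-off.

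The size is unknown. Under the assumed 5% to 20% reclassification at a true rate of 40%, the chance of passing the gate rises from 17.9% to between 22.3% and 38.2%. This assumes that every reclassification runs from negative to positive; the documents support neither that direction nor any particular rate. A reader might infer that the endpoint is already compromised. The documents show only an open route to bias, not that it would be taken. This is a cheap improvement and not a fault that invalidates the design.

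**What to change.** State in Section 12.0 that:

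1. the readers who set the active-lesion list are masked to the tracer scan and its report;
2. the list, including any consensus on conventional images, is completed, dated and locked from conventional imaging and clinical data before those readers see tracer images;
3. any later change is logged with its reason and used only in a sensitivity analysis.

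Reconcile the patient-level definitions in Sections 9.3 and 14.2, so that it is clear which rule the locked list serves.

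The cost is a fixed reading order and one dated form. The readers stay the same, and no new procedure is needed. Where conventional imaging is done after entry, the list-setters' view of the tracer scan waits until that imaging has been read.
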